DLBCL DISEASE: ASSESSMENTS INCLUDING CENTRAL AND LOCAL LABORATORY ASSESSMENTS															
Immunoglobulins (IgA, IgG, IgM)	8.3.6.2	Also see Table 10-1	X												
Tumor biopsy	8.8.1	A portion of biopsy will be used for biomarker evaluations. Also see Table 1-11	X						X  (C3)				X 		
DLBCL with bone marrow involvement: bone marrow aspirate/biopsy	8.2.3.2	Biopsy obtained as routine standard of care may be used, if taken up to 42 days before C1D1. A portion of bone marrow aspirate/ biopsy will be used for biomarker evaluations. Also see Table 1-11 .	X	Bone marrow biopsy plus aspirate is required for confirmation of an observed radiologic CR; should be done within 30 days of the initial documentation of radiologic CR								X			
FDG-PET-CT/ CT/MRI	8.2.3.1		X	Required at: C2 (W6), C3 (W12), C5 (W18), C6 (W24), then every 24 weeks thereafter (Cycle 12, 18, 24, etc.) until confirmation of disease progression, start of new anti-cancer therapy, withdrawal of consent, or death, whichever comes first								X			

Cycle(s)	Pro- tocol Section	Notes	Screen- ing	Q1W (Weekly)					Q2W		Q4W	UNS	End of Treat- ment	Safety Follow- up 	Survival Status/ contact 
				Cycle 1-2					Cycles 3-6		Cycle 7 onward				
Cycle Day			D -21 to D -1	D1 	D2 (C1 only)	D8	D15	D22	D1	D15	D1		ASAP after last dose	30d after last dose	Q3M
Visit Window							±3d		±3d		±3d		+7d	+7d	±7d
MRI or CT of the brain	8.2.3.1	Perform at Screening only if brain involvement is suspected	X	May be performed during the trial if clinically indicated.											
Response assessment	8.2.3	Response required per efficacy assessment time points		Required at: C2 (W6), C3 (W12), C5 (W18), C6 (W24), then every 24 weeks thereafter (Cycle 12, 18, 24, etc.) until confirmation of disease progression, start of new anti-cancer therapy, withdrawal of consent, or death, whichever comes first								X			
END OF TREATMENT															
New anti-cancer therapy	7.1.1													X	X
Survival Status	7.1.2														X

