**Table 5: Analysis visit windows for efficacy summary listings in R/R DLBCL**

Analysis period	Target day (visit window per protocol)	Analysis visit window	Label on output
Baseline	1 (pre-dose C1D1)	Last data point prior to dosing	Baseline
Scheduled on-treatment disease assessments Week 6,	42 ( $\pm 3$ )	1 to 63	Week 6
	84 ( $\pm 3$ )	64 to 105	Week 12

12, 18, and 24, then every 24 weeks thereafter	126 ( $\pm$ 3)	106 to 147	Week 18
	168 ( $\pm$ 3)	148 to 252	Week 24
	336 ( $\pm$ 3)	253 to 420	Week 48
	...	...	...
Unscheduled	-	-	Unscheduled <Day x>
End of treatment	-	-	End of treatment

Response assessments should be performed until confirmation of disease progression, start of new anti-cancer therapy, withdrawal of consent, or death, whichever comes first.

Details on how to slot subject data that systematically is performed off schedule is provided in the ADaM specification, but no data should be disregarded for efficacy evaluations due to this windowing.

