**Table 8: Censoring scheme for time to event variables**

Situation	Date of Progression or Censoring	Censoring Rule
Incomplete or no baseline assessments	C1D1, or date of randomization	Censored
No documented PD or death prior to analysis data cutoff, trial discontinuation, start of new anti-cancer treatment	Date of last valid tumor assessment with no documented PD before the situation*	Censored
Documented PD between adequate** assessment visits	First date of assessment demonstrating documented PD	Event
Death before first response assessment	Date of death	Event
Death between adequate** assessment visits	Date of death	Event
Death or documented PD after two or more consecutive missed visits***	Date of last valid tumor assessment prior to the missed visits*	Censored

\*Excluding response assessments with NE as overall time point response. If no such assessment exists, the censoring date will be C1D1.

\*\* No more than one missed visit, no anti-cancer therapy etc. before the death or documented progression.

\*\*\* Please refer to the DPS for the definition of two missed scans.

Clinical progression (as recorded in eCRF) does not constitute documented progression and will cause censoring (unless documented progression was recorded before clinical progression).

DOR will be estimated using the KM method and the result will be displayed graphically. The number and percentage of subjects with event or censoring will be reported. Median DOR (months) with associated 95% CI as well as first and third quartiles and range will be provided.

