#### **5.4.5 PFS**

Progression-free survival (PFS, months) is defined as the time from C1D1, or randomization, to first documented PD or death due to any cause, whichever occurs earlier (see Table 8 for censoring rules). PFS will be derived for all subjects and analyzed using similar methods as DOR.

PFS event-free rate at a landmark time T is defined as the probability that a subject has not progressed and is alive at time T. (Subjects with an intermittent event prior to the landmark will not be a part of the analysis.) PFS event-free rates at 6, 9, and 12 months (or later times if available) will be presented along with 95% CI.

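### In the R/R DLBCL cohort the 9-month PFS rate falls inside a 24-week gap between scheduled scans and is biased upward

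*SAP*

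**What the plan says.** Protocol Table 1-7 sets DLBCL imaging and response assessment as follows: "Required at: C2 (W6), C3 (W12), C5 (W18), C6 (W24), then every 24 weeks thereafter (Cycle 12, 18, 24, etc". SAP Table 5 gives the same schedule ("12, 18, and 24, then every 24 weeks thereafter"), with target days 42, 84, 126, 168 and then 336.

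SAP 5.4.5 defines PFS by "first documented PD or death due to any cause, whichever occurs earlier". Table 8 dates a documented progression at the "First date of assessment demonstrating documented PD" and a death at its own date. Under the same table, "Clinical progression (as recorded in eCRF) does not constitute documented progression and will cause censoring", unless a documented progression came first.

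SAP 5.1 specifies Kaplan-Meier estimation. SAP 5.1.2 uses exact dates and keeps the visit windows mainly for display. SAP 5.4.5 then fixes the landmarks: "PFS event-free rates at 6, 9, and 12 months (or later times if available) will be presented along with 95% CI". There is no exception for DLBCL, and SAP Section 1 says the methods are the same across diseases. No interval-censored PFS analysis is described.

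**The concern.** A landmark rate reads as the proportion alive and progression-free at that time. That is close to true when a scan has just taken place. In DLBCL the 9-month landmark comes 15 weeks after the last scheduled scan and 9 weeks before the next, and progression in between is dated late, never early. The 9-month figure is therefore roughly the Week 24 figure, less deaths and any progressions caught by unscheduled imaging. The error is systematic, so the planned 95% confidence interval does not account for it. RRMM is evaluated every 28 days and AML every cycle, so neither has a comparable gap.

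**Working it through.** **Stated figures.** The plan gives no PFS median, rate or precision for DLBCL, so there is nothing on this point to reproduce. The cohort's Simon design (at least 5/20, then at least 13/40; 20% vs 40%) does recompute to the stated 4.04% and 85.39%, but it concerns ORR.

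**Placing the landmarks**, at 30.4375 days per month (the conversion in SAP 5.5.1.1):
- 6 months = day 182.6, 2.1 weeks after the Week 24 scan.
- 9 months = day 273.9, 15.1 weeks after Week 24 and 8.9 weeks before Week 48.
- 12 months = day 365.3, 4.2 weeks after the Week 48 scan.

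**Base case.** Assume exponential PFS, a share q = 20% of PFS events being deaths without progression, no censoring, no unscheduled scans, and no deaths after an undetected progression before Week 48. Of the true events between day 168 and day 274, only the deaths appear on the curve. Hence

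expected rate at 9 months = S(168) − q × [S(168) − S(274)], and excess = (1 − q) × [S(168) − S(274)].

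For a 6-month median, S(168) = 0.5^(168/182.625) = 52.9% and S(274) = 0.5^1.5 = 35.4%. The excess is 0.8 × 17.5 = 14.0 points, so 49.4% is expected against a true 35.4%.

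| Median PFS (months) | True 9-month rate | S(168) | Excess (points) | Expected reported rate |
|---|---|---|---|---|
| 3 | 12.5% | 27.9% | 12.3 | 24.8% |
| 4 | 21.0% | 38.4% | 13.9 | 34.9% |
| 6 | 35.4% | 52.9% | 14.0 | 49.4% |
| 9 | 50.0% | 65.4% | 12.3 | 62.3% |
| 12 | 59.5% | 72.7% | 10.6 | 70.1% |

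**Relaxing the base case**, by simulation over the same medians and death share:
- Counting deaths after undetected progression at their own date, with an assumed median survival of 4 to 6 months after progression: excess about 8 to 11 points.
- Half of gap progressions promptly scanned (same day to three weeks later, with or without those later deaths): about 4 to 8 points.
- 80% scanned, three weeks after progression, with those later deaths counted: about 3 to 4 points. Same-day detection would give about 2.

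The rate was too high in every scenario.

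**The other landmarks.** The same formula at 6 months, 0.8 × [S(168) − S(182.6)], and at 12 months, 0.8 × [S(336) − S(365.3)], gives about 1 to 3 points. Censoring is a separate matter at 12 months. A clinical progression in the gap without a documenting scan is censored at the last valid assessment, usually Week 24. With a 6-month median, 15% of events as deaths and half of gap progressions censored in this way, the 12-month rate comes out at 34% against a true 25%.

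**The case against.** The strongest reply has four parts.

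- **The gap is unscanned by schedule, not unobserved.** Protocol 1.3 allows unscheduled assessments, and Table 1-7 marks imaging in the unscheduled column. From Cycle 7, constitutional symptoms, ECOG status and physical examination are still scheduled every 4 weeks on treatment, and Protocol 8.2.3 makes them part of DLBCL evaluation. Protocol 2.1.1.3 describes an aggressive disease with short survival after treatment failure, so some undetected progressions will enter as deaths. This stands. It is why 11 to 14 points is close to a worst case, but it shrinks the bias without reversing it.
- **The estimate is imprecise anyway.** With 40 subjects and a true rate of 35.4%, the 95% half-width is about 1.96 × √(0.354 × 0.646/40) = 14.8 points. This is also true, but the interval would be centred on the wrong value.
- **The plan is already hedged.** SAP 5.1 says landmark rates may be presented, and Protocol 9.4.3.4 allows descriptive statistics if events are few. A plotted curve would also show steps at Weeks 24 and 48. But 5.4.5 is the specific text and says the rates will be given, and a tabulated rate carries no sign of the gap.
- **Nothing turns on the number.** A reader might infer that an artificial plateau between 6 and 9 months would mislead the DLBCL signal decision. The documents do not support that. Protocol 9.5.2 and SAP 5.7.2 rest the criterion on ORR (5/20 and 13/40), with the interim decision on the totality of the data. PFS is secondary, there are no hypotheses, and Protocol Section 9 plans no comparisons between cohorts.

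**Conclusion.** The point holds for one estimate. The 9-month DLBCL PFS rate is biased upward by the scan schedule combined with the dating rule. The direction follows from the documents. The size rests on assumptions they do not supply: exponential PFS, medians of 3 to 12 months, 20% of events as deaths, 4 to 6 months' median survival after progression, and the share of progressions scanned promptly. Across these the excess runs from about 11 to 14 points at the unfavourable end down to about 3 to 4 points if 80% are promptly scanned.

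Two stronger readings should be resisted. The first takes the top of the range as the expected size, which would require that no unscheduled scans and no deaths after undetected progression occur before Week 48. The second takes the 12-month rate as clean because a scan precedes it. Scan timing alone adds only 1 to 3 points there, but censoring of clinical progression can add more, so that rate should be read alongside the number so censored.

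**What to change.** In SAP 5.4.5, add an exception for the R/R DLBCL cohort: omit the 9-month PFS rate and report only landmarks that follow a scheduled scan, either 6 and 12 months or times just after Weeks 24 and 48. An interval-censored (Turnbull) PFS estimate could be added as support; with 20 to 40 subjects and a descriptive endpoint it is optional.

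The cost is a sentence of SAP wording and one fewer landmark for this cohort, plus one output if the optional estimate is taken up. The imaging schedule and patient management are unaffected.

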#### **5.4.6 OS**

Overall survival (OS, months) is defined as time from C1D1, or randomization, to death due to any cause, will be analyzed using the Kaplan-Meier method. The subjects who are alive or with no observed death will be censored at last contact date.

Median OS with associated 95% CI as well as first and third quartiles and range will be provided. Survival rates at 6, 9 and 12 months (or later times if available) will be presented along with 95% CI.

#### **5.4.7 TTNT**

Time to next therapy (TTNT, months) for subjects in the Expansion Part B is defined as the time from randomization to the start of subsequent anti-cancer therapy. Death due to PD without start of subsequent therapy will be considered as an event. Subjects who withdrew consent to study or are lost to follow up or die due to causes other than disease progression will be censored at their last disease assessment.

TTNT will be derived for all subjects and analyzed using similar methods as DOR.

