- SPEP, UPEP, serum FLC, serum IFE, and urine IFE should be performed preferably within 14 days prior to C1D1 (during Screening), and on C1D1. Subsequent on-treatment SPEP and UPEP are to be performed every 28 (±3) days on the scheduled assessment day. All responses based on biochemical investigations, including PD, require 2 consecutive assessments by central lab for confirmation. Once PD is confirmed, subsequent disease assessments are not required. Additional aliquots will be collected for IFE reflex testing, in case of potential interference of GEN3014 or daratumumab with interpretation of M-protein levels.
- Perform serum FLC and serum/urine IFE at Screening and when CR is suspected or maintained. Perform serum FLC on Day 1 of every cycle for all subjects.
- A skeletal survey, including cranium, is required during Screening. Results from skeletal survey performed within 42 days before C1D1 as routine follow up for subject's disease state may be used. Additional imaging will be performed as clinically indicated.

11. At Screening, fresh bone marrow aspirate and biopsy are required for clinical assessment of disease. At baseline (Screening) only, non-decalcified diagnostic slides (bone marrow aspirate, touch preparation or clot selection) or FFPE block (clot section only, no bone marrow biopsy) up to 42 days prior to enrollment may be collected for MRD assessment if the fresh aspirate fails to calibrate during testing.
12. Bone marrow aspirate and/or biopsy will be conducted locally to confirm CR/sCR. A portion of bone marrow aspirate will be sent to central laboratory to confirm CR/sCR, assess MRD (at time of suspected CR/sCR, and at 6, 12, 18, 24, and 30 [ $\pm$ 1] months post C1D1 for subjects who achieve CR/sCR and remain on trial), and for other biomarker evaluations. If 1 of the time points for collection to assess MRD occurs within 1 month of suspected CR, a repeat bone marrow will not be requested. The bone marrow tests at CR/sCR and beyond will only be required if subject's response is near CR or better by blood and urine evaluations. If clinically feasible, a bone marrow aspirate will also be performed at End of Treatment/PD.

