### **8.2.1 Efficacy Assessments for RRMM**

Assessment of tumor response and disease progression will be conducted in accordance with the IMWG Response Criteria (Kumar et al., 2016). Disease evaluations will include measurements of myeloma proteins, bone marrow examinations, skeletal surveys, assessment of extramedullary plasmacytomas, and measurements of  $\beta$ 2-microglobulin, albumin, and serum calcium corrected for albumin. Disease evaluations must be performed every 28 days ( $\pm 3$  days) as defined in Table 1-1 (Dose Escalation), Table 1-5 (Expansion Part A [GEN3014 Single Cohorts]), and Table 1-12 (Expansion Part B [Randomized H2H]) until disease progression according to IMWG Response Criteria (see Section 10.9). All response categories require 2 consecutive assessments made at any time, prior to initiating a new therapy. As minimal residual disease (MRD) will also be evaluated, these criteria will be included per IMWG Response Criteria (Section 10.9); see Section 8.8.3 for more information on assay and methodology.

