#### ***9.4.3.6 Time to Next Therapy***

Time to next therapy (TTNT) for subjects in the Expansion Part B is defined as the time from randomization to the start of subsequent anti-cancer therapy. Death due to PD without start of subsequent therapy will be considered as an event. Subjects who withdrew consent to study or are lost to follow up or die due to causes other than disease progression will be censored at their last disease assessment.

TTNT will be summarized similarly to OS.

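### TTNT is censored at the last disease assessment, so the known therapy-free time after progression is dropped for subjects who withdraw, are lost or die of other causes

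*SAP*

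**What the plan says.** SAP 5.4.7 defines TTNT in Part B as "the time from randomization to the start of subsequent anti-cancer therapy". Death from progression before any next therapy also counts as an event. Subjects who withdraw consent, or who are "lost to follow up or die due to causes other than disease progression will be censored at their last disease assessment", are censored. Protocol 9.4.3.6 has the same sentence: those who "die due to causes other than disease progression will be censored at their last disease assessment". The SAP was written against Amendment 3, but the Amendment 5 protocol keeps the rule, so this is not a version difference.

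On when disease assessments end, Protocol 8.2.1 has myeloma evaluations run "until disease progression according to IMWG Response Criteria", and a footnote to Table 1-12 adds: "Once PD is confirmed, subsequent disease assessments are not required".

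On when next therapy is recorded, the new anti-cancer therapy row of Table 1-12 is marked only under the safety follow-up visit and the 3-monthly survival contact. Protocol 7.1.2 continues those contacts until death or withdrawal.

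Neither TTNT section gives a censoring date for a subject who is alive without next therapy at data cut-off. The SAP says "TTNT will be derived for all subjects and analyzed using similar methods as DOR", and DOR uses Table 8. The protocol says "TTNT will be summarized similarly to OS".

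**The concern.** The censoring date follows the disease-assessment schedule, but the event occurs on a different schedule. For a progressed subject, the last disease assessment is about the date of progression. That is when the subject becomes likely to start a new therapy and when the follow-up that records it begins.

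Post-progression follow-up is then used unevenly. If a progressed subject starts new therapy or dies of progression, the event is placed at its true date. If a comparable subject is seen therapy-free over the same months and is then lost, withdraws or dies of another cause, those months are removed. Events stay in while event-free time leaves the risk set. The censoring date is set back using something learned later, and this is not the non-informative censoring that Kaplan-Meier needs. The estimated TTNT curve is pushed down.

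TTNT is one of the endpoints for the Part B objective that sets GEN3014 IV against daratumumab SC, so both arms' curves will be read side by side.

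**Working it through.** The documents give no median, event count or power for TTNT, so there is no stated figure to reproduce. The check sets the passages side by side, does the follow-up arithmetic, and illustrates the size under stated assumptions.

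**1. Direction.** Take a subject who progresses, has no next therapy, and is later lost.
- Last disease assessment: about the date of progression (Protocol 8.2.1, Table 1-12).
- Last date known therapy-free: the last safety or survival contact (Table 1-12, Protocol 7.1.2).
- Date used by the rule: the first of these.

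The time between the two dates leaves the denominator of the hazard. No event is removed with it, so the hazard can only rise and TTNT can only shorten. For OS, the SAP (5.4.6) uses the last contact date, which avoids this.

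**2. One subject, using the protocol's own durations.** Protocol 4.4.1.3 gives 21 days of screening, 4 months of treatment and 17 months of follow-up: 21/30.4375 + 4 + 17 = 0.69 + 4 + 17 = 21.7 months, which agrees with the stated 22. If a subject progresses at month 4, is therapy-free at every contact to month 21 and is then lost, the rule censors at month 4. Time dropped: 21 − 4 = 17 months, or 17/21 = 81%. This is an extreme for one subject.

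**3. Illustrative simulation.** The assumptions, none of them in the documents, are: exponential time to progression with median 4 or 8 months; mean gap from progression to next therapy 1, 3, 6 or 12 months; loss, withdrawal or other-cause death at 0.01, 0.03 or 0.05 per month; cut-off uniform over 6 to 30 months; assessments every 28 days until progression; 200,000 subjects per scenario. The reference censors at last contact and treats therapy status as known up to that date.

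| Median PD / mean gap / monthly loss | Last contact | Rule, three named groups | Rule, also at cut-off |
|---|---|---|---|
| 8 / 1 / 0.01 | 9.0 | 9.0 | 8.9 |
| 4 / 6 / 0.03 | 9.9 | 9.4 | 8.7 |
| 4 / 12 / 0.05 | 14.6 | 12.8 | 10.7 |
| 8 / 12 / 0.05 | 19.9 | 18.2 | 15.6 |

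(Median TTNT, months.) Over all 24 scenarios the median falls by 0.0 to 1.8 months when the rule covers only the three named groups. It falls by 0.1 to 4.3 months if subjects event-free at cut-off are also set back to the last assessment. The mean time dropped per subject in the named groups is 0.5 to 3.8 months.

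**4. Subjects event-free at cut-off.** Following the SAP's reference to DOR leads to Table 8, whose date for subjects without an event is "Date of last valid tumor assessment with no documented PD before the situation". The situations listed for that row include the start of new anti-cancer treatment, which is the TTNT event itself, and the table counts documented progression as an event, which TTNT does not. Following the protocol's reference to OS suggests last contact. The two cannot both be applied.

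**The case against.** The strongest case against is that the effect is narrow. The sentence covers three groups only, and within them the date moves materially only for subjects who had progressed and had not started new therapy. Loss to follow-up requires at least three documented contact attempts (Protocol 7.3), and survival status can be obtained by several routes (7.1.2). There are no hypotheses, and no test or hazard ratio is specified for TTNT. All of this stands; it limits the size, not the direction.

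A reader might infer more than the text supports:
- That next-therapy starts found in follow-up are ignored. They are not: the event is the start of therapy whenever it occurs. Only event-free time in censored subjects is lost.
- That 81% is typical. The 4 and 17 months are estimated treatment and follow-up periods, not a gap from progression to next therapy. Protocol 2.1.1.1 cites a median survival of 8 months in patients refractory to a PI and an IMiD. The primary analysis falls at latest 6 months after the last first dose, so late enrollees could not have 21 months of follow-up by then.
- That the arm comparison is biased. That needs the loss rate, other-cause deaths or the progression-to-therapy gap to differ by arm, and the documents give no sign of it.
- That date of death is always the right censoring date for other-cause deaths. Contacts are 3-monthly and survival status may come from registries, so therapy status just before death may be unknown.

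**Conclusion.** The point holds in this limited form. Applied as written, the rule drops the known therapy-free time after progression of subjects who withdraw, are lost or die of other causes, and keeps all later events. Estimated TTNT is therefore too short. The size depends on the gap from progression to next therapy and on the rate of loss, neither of which is in the documents. Under the assumed ranges the median moves by 0.0 to 1.8 months for the named groups. The range up to 4.3 months applies only if the SAP's reference to DOR is read as setting event-free subjects at cut-off back to the last assessment, and the protocol's reference to OS points the other way. Any distortion of the arm comparison is conditional on a difference between arms. Because TTNT is secondary and descriptive, no error rate or sample size changes. It should still be corrected, because the rule is explicit in both documents and conflicts with the way next therapy is followed.

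**What to change.** In Protocol 9.4.3.6 and SAP 5.4.7, replace the censoring sentence with one rule for every subject without a TTNT event: censor at the last date, on or before data cut-off, at which the subject was known to be free of subsequent anti-cancer therapy. For deaths not due to progression, use the date of death if therapy status is known to that date, and otherwise the last contact at which it was known. State that Table 8 does not apply to TTNT, and replace the DOR and OS references with this rule so that the two documents agree.

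The cost is a sentence or two in each document. The follow-up contacts are already scheduled. Table 1-12 shows that new therapy is collected at them, but not that a dated negative is recorded when there is none, so check that the eCRF captures one.
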